9. RESEARCH METHODS

9.1 STUDY DESIGN

This is an observational cohort study based on existing data.

BOEHRINGER INGELHEIM Group of Companies**NIS Protocol Template****Study number: 1484.0014****Page 12 of 30****Document number: <insert>****9.1.1 Study population**

Study inclusion criteria: All patients ≥ 50 years, with a GA diagnosis in at least one eye, including in the [REDACTED] database identified during the study period (January 2015 to April 2023).

Exclusion criteria: Patients without the information of laterality will be excluded.

No other exclusion criteria are applied for the identification of the study population and description of the patients and eye at baseline.

Additional note:

For certain analysis the patient population will be restricted to those with at least 12, 24, 36, 48, or 60 months of history following diagnosis of GA. For the analysis requiring a VA reading, a restriction to those patients with valid VA readings at the index diagnosis and the respective follow-up times will be applied.

For analysis estimating the size of the GA population relative to other retinal diseases, the same timeframe requirements that the study population will be applied. In this population, any patient in the database will be eligible, and the diagnosis of DME, DR or other conditions may be used for subgroup comparisons.

Primary Disease Definitions

In the [REDACTED] Database, retinal and other diseases are identified using the International Classification of Diseases (ICD), Tenth Revision, Clinical Modification. ICD 10 codes were launched in the USA in October 2015, and are the only version of ICD codes with adequate descriptions of GA and dry AMD severity. As such, only ICD 10 codes will be analyzed in this study and the study period defined above is directly related to the launch of ICD 10 plus a small buffer allowing for physician familiarity.

These codes are entered by the physician at patient visit, with an associated laterality. This, along with the ICD 10 laterality is used in combination to confirm in which eye the disease is occurring. For this study, a patient eye will be considered to have the study disease so long as there is an accompanying ICD code. The primary study diseases to be analyzed are dry AMD, GA and wAMD, and will be identified using the ICD codes in Table 1 below.

Table 1. Study disease definitions-codes.

Study Disease Definitions			
	Dry AMD*	Dry AMD with GA*	wAMD*

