Prevalent visit – all visits following the incident visit in patient eye history while identified with GA in the [REDACTED] database. Prevalent visits may occur year after year throughout the patients' journey.

Study period

Patients will be identified from January, 2015 to April, 2023.

Selection period: Eligible patients must have at least one GA diagnosis between October 2015 and April 2023. The date of the first GA diagnosis will be considered as index date. For all follow up analysis, eligible patient eyes should be divided in those with at least 12, 24, 36, 48 and 60+ months of follow up. follow up requires multiple visits spanning over the outlined durations and total follow up is defined as the time between incident diagnosis and the final visit in the dataset.

BOEHRINGER INGELHEIM Group of Companies**NIS Protocol Template****Page 14 of 30****Study number: 1484.0014****Document number: <insert>**

Follow-up period: up to 60-month period following the index diagnosis date of GA (exploratory follow-up of 1, 2, 3, 4, 5 years may be run as cutoff points)

Pre-selection period: January 2015-September 2015. This period will be used to identify patients who have dry AMD using ICD9 coding, and will help to assign patients into the incidence or prevalence status.

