9.5 STUDY SIZE

During the development of the protocol and while running the projects viability, a feasibility was run on the database identifying both patients and eyes with Dry AMD, and specifically with GA. This analysis was run using only ICD 10 codes and with the use of exam notes. Actual population counts are subject to change based on the dataset available at first data run, but all analysis will be based on the assumption that population sizes are relative to these numbers.

GEOGRAPHIC ATROPHY (PERIOD >=2016) (ICD 10 + Exam Notes)

# of Patients	72,718
# of Eyes	113,408
Avg months of follow-up	22
# of Patients with visits after 3 years	20,503
# of Eyes with visits after 3 years	31,647

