An additional analysis will be made to extrapolate the prevalent results to a national – US-level. For that analysis, the prevalence of GA will be considering all patients seen by a retina specialist in the given year. With this metric, estimation on a national level will be done using an estimation of all practicing US retina specialists.

When analyzing the rate of progression from dry AMD to GA, a conversion analysis will be done. This will include the overall rate of dry AMD eyes developing GA, along with a Kaplan Meier analysis assessing the rate of conversion over time. This analysis will track progression by month from diagnosis, censor any patient at the final visit in the database, and identify the incident GA diagnosis as an event.

Analysis for objectives:

To evaluate patients' management (i.e. patients visits and procedures) over the study period.

BOEHRINGER INGELHEIM Group of Companies**NIS Protocol Template****Page 24 of 30****Study number: 1484.0014****Document number: <insert>****Patients' management**

All visits, treatment, checkups, procedures, and other will be summarized across the duration of the study time frame as well as between the index diagnosis and at the 12 (24, 36, 48, 60) month follow up period.

An additional sub analysis will be conducted to evaluate the changes in the frequency of patients visits or procedures, checkups, after the third quarter of 2021 and after [REDACTED].

Summary will include descriptive statistics; continuous variables will be described by absolute numbers, the mean (SD), median and range, while categorical variables will be described using frequency and proportion. Absolute numbers (n), and correspondent percentage (%) of the variables (either eyes or patients as appropriate) will be always included in the description of the results.

Analysis for objective:

To describe and compare patients' characteristics in different progression subgroups (i.e. those that develop eCNV/those that not), of the overall GA population.

The following groups will be evaluated to better understand progression:

1. Patients that [REDACTED]

vs. those that do not in the 1, 2, 3, 4 and 5 years of follow up period.

2. Patients that [REDACTED]

vs. those that do not in the 1, 2, 3, 4 and 5 years of follow up period.

3. Patients with subfoveal lesion location vs. those with extrafoveal lesion location.

For this subgroup of patient's characteristics will be described and compared.

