Subgroups will be compared against one another to identify any differences in populations leading to progression. The characteristics will be extracted at the time of assignation to the group i.e. patient do not [REDACTED] in year one is contributing with his characteristics extracted at year 1 to the group (no progressors), that patient [REDACTED] at year 5 is contributing with his characteristics extracted at year 5 to the progressor group.

Summary will include descriptive statistics; continuous variables will be described by absolute numbers, the mean (SD), median and range, while categorical variables will be described using frequency and proportion. For discrete demographics or clinical characteristics, chi-squared test of proportion will be done to assess meaningful difference (standardized mean difference SMD may be used as an alternative), while continuous variables will be analyzed using SMD. Following univariate analysis on each metric, a multivariate logistic regression model will be run including relevant metrics identified in the univariate analysis.

Additional information on the analysis is described below:**Patient Demographics (at index and follow up):**

BOEHRINGER INGELHEIM Group of Companies**NIS Protocol Template****Page 25 of 30****Study number: 1484.0014****Document number: <insert>**

N (%); Age, gender, region; Bilateral status, other eye related diagnosis in study and fellow eye; Distribution by months of follow up; Concomitant illnesses (diabetes, cataract, etc.); Lesion location and size (along with % capture rate)

Progression : Progression of GA over time; Fellow eye AMD status; [REDACTED] (study and fellow eye) Mean (median/IQR) time to conversion; Conversion to GA (fellow eye) Mean (median/IQR) time to conversion; Proportion of patients with wAMD and GA (N, %)

[figure not shown]
Treatment Characteristics (follow up): Number of visits over time; Number of treatments over time, Mean (median) time to study treatment; Type of treatment – Anti-VEGF, Laser, Combination, Mean (median) time on therapy

New cases occurrence and prevalent cases of GA (stratified by index year): N (%)

- Age, gender
- Distribution by months of follow up
- Calculation to the % of patients attending the retinal specialist over the same time period for other retinal conditions i.e. wAMD, DR, dry AMD or DME.

Visual Acuity Outcomes

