9.9 LIMITATIONS OF THE RESEARCH METHODS

As with real world data entered during patient encounters, there are limitations due to the entry process and general operations of both physicians and clinics. The [REDACTED] database includes only data from visits that occurred at the practices contributing to the database. Anything occurring during visits to a retina specialist/ophthalmologist in a different practice, state, country etc. is not captured.

[REDACTED] does receive information on previous history, referrals, etc. from overall patient history fields in attempt to gain insights on potential previous physicians, however [REDACTED] completely relies upon the physician to enter these data. This is a limitation of the study regarding the incidence and prevalence of the study diseases.

Retinal specialists are the primary specialty that will observe and treat all forms of AMD. However, there is a portion of mild dry AMD patients who are being observed by their general ophthalmologist. As this study will focus on GA specifically, there should not be a concern with underrepresentation in the database, as it is the most severe form of dry AMD. Out of the 1.6 million eyes with 1+ visit to in the [REDACTED] in 2022, dry AMD was the most prominent disease with ~180,000 eyes, twice as large as those with wAMD. While this study will identify newly diagnosed cases of GA and wAMD, there is a possibility that a patient was diagnosed prior by an ophthalmologist or other retina specialist. As these are severe versions of AMD that are handled only by retina specialists in the USA, it is a limitation that must be addressed.

Prevalent cases are less affected as per the study definitions they are being seen over a multiple year span in the same dataset. While it is possible, they are seeing other healthcare

BOEHRINGER INGELHEIM Group of Companies**NIS Protocol Template****Study number: 1484.0014****Page 27 of 30****Document number: <insert>**

professionals during this time frame, they are continuing to visit their retina specialist for follow up. Patients who leave the panel for any number of reasons (death, moving, poor experience) are only able to be identified as lost to follow up. No other claim can be made on these cases, and for the study purposes they would no longer be included in any analysis from that point onwards.

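### The whole-period summary of visits and treatments, and the before/after Q3 2021 comparison, name no person-time denominator, so counts mix length of observation with intensity of care

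*Combined protocol and SAP*

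**What the plan says.** One secondary objective (section 8) is to evaluate patient management, meaning visits and procedures, over the study period. Section 9.7.1 gives two time frames in a single sentence. The first is the whole period: "All visits, treatment, checkups, procedures, and other will be summarized across the duration of the study time frame". The second is a set of windows: "as well as between the index diagnosis and at the 12 (24, 36, 48, 60) month follow up period". The statistics named are the same for both: "continuous variables will be described by absolute numbers, the mean (SD), median and range". The list of treatment outputs repeats the idea as "Number of visits over time; Number of treatments over time, Mean (median) time to study treatment", and adds mean (median) time on therapy without defining it. A sub-analysis looks for changes in the frequency of visits, procedures and checkups after the third quarter of 2021.

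On follow-up, section 9.1.1 says that for all follow-up analyses "eligible patient eyes should be divided in those with at least 12, 24, 36, 48 and 60+ months of follow up", while its additional note says that for certain analyses, not named, the population will be "restricted to those with at least 12, 24, 36, 48, or 60 months of history following diagnosis of GA". Follow-up runs from the incident diagnosis to the final visit. Section 9.9 adds: "Patients who leave the panel for any number of reasons (death, moving, poor experience) are only able to be identified as lost to follow up". Such patients leave all analyses from that point. Section 9.3.2.2 says that physician care is assessed yearly from the incident date and that visit burden is tracked year over year.

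**The concern.** A total count is the product of how often a patient is seen and how long the patient is observed. The index date can fall anywhere from October 2015 to April 2023, and observation ends whenever the patient stops attending. A mean number of visits over the whole study period therefore describes a mixture of observation times as much as it describes care. The before/after comparison meets the same difficulty: a frequency needs a time base, and the two calendar periods differ greatly in length.

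At stake is the answer to a descriptive secondary objective, and any conclusion that retina specialists changed their practice after Q3 2021. The plan recognises short, unequal follow-up where progression is concerned: section 9.9 suggests Kaplan-Meier, and section 9.7.1 censors at the final visit for conversion from dry AMD to GA. It says nothing equivalent for visits, treatments or time on therapy.

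**Working it through.** The protocol states no expected visit or treatment count, so there is no planned figure to reproduce. The visit rate below is an assumption (2, 4 or 6 per year); the other inputs come from the document.

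**1. How unequal is observed time?** Section 9.5 gives "Avg months of follow-up" as 22, with 72,718 patients and 20,503 having visits after 3 years.
- Patients with visits after 3 years: 20,503 / 72,718 = 28.2%. Eyes: 31,647 / 113,408 = 27.9%.
- Section 9.9 gives a mean of 1.9 years. 22 / 12 = 1.83 years, and the two agree by rounding if the true mean is 22.2 to 22.5 months.
- Longest possible follow-up to April 2023: 88 months from January 2016, 16 months from January 2022.

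**2. Whole-period count at one constant rate.** Expected count = rate × months / 12.

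| Visits per year (assumed) | 12 months | 22 months | 36 months | 60 months |
|---|---|---|---|---|
| 2 | 2 | 3.7 | 6 | 10 |
| 4 | 4 | 7.3 | 12 | 20 |
| 6 | 6 | 11 | 18 | 30 |

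Intensity of care is identical along each row. Ordering can also reverse: 4 per year for 12 months gives 4 visits, while 2 per year for 36 months gives 6.

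**3. Share of the spread due to follow-up.** A simulation with Poisson visits at 4 per year and exponential follow-up (mean 22 months, capped at 88) gave a mean count of 7.2 and an SD of 7.3. About 86% of the between-patient variance came from follow-up length. Total visits over total time returned 4.0 per year. Splitting the variance into 45.6 from follow-up and 7.2 Poisson, and rescaling to other rates, gives:
- 2 per year: 11.4 / (11.4 + 3.6) = 76%.
- 6 per year: 102.6 / (102.6 + 10.8) = 90%.

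The exponential form puts 19% of patients beyond 36 months, against 28% in the feasibility run, so these shares are indicative only.

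**4. The fixed windows.** Under the same assumptions at 4 per year, patients observed for all k months have 4k/12 visits on average. If everyone enters the window, the mean is (4/12) × 22 × (1 − exp(−k/22)).

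| Window | Only patients observed throughout | Everyone | Share observed throughout |
|---|---|---|---|
| 12 months | 4 | 3.1 | 58% |
| 24 months | 8 | 4.9 | 34% |
| 36 months | 12 | 5.9 | 19% |

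With the restriction, the window returns the true value when the rate is constant. Without it, the shortfall grows with the window.

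**5. Before and after Q3 2021.** October 2015 to September 2021 is 72 months; October 2021 to April 2023 is 19 months; 72 / 19 = 3.8. A patient observed throughout at 4 per year has 4 × 72/12 = 24 visits before and 4 × 19/12 = 6.3 after, with no change in care. A patient indexed in January 2021 has at most 9 months before and 19 after, so the distortion runs the other way. The net direction depends on the mix of index dates, which the document does not give.

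**6. The denominator itself.** Follow-up ends at a visit, so the events being counted fix the time. Take a patient indexed 16 months before the data cut, seen again at months 3 and 6 and never after. Measured to the last visit, the rate is 2 / 0.5 = 4 per year. Measured to the data cut, it is 2 / (16/12) = 1.5. A patient with only the index visit has zero time. A rate to the last visit is therefore biased upward, and more so if the index visit is counted.

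**The case against.** The strongest reply is that the plan does not rest on whole-period totals. The same sentence in section 9.7.1 adds windows of 12 to 60 months, section 9.1.1 divides eyes by minimum follow-up for all follow-up analyses, and section 9.3.2.2 promises yearly tracking. This stands. A reader might infer that the whole patient-management result reflects time under observation; the documents do not support that, because in patients observed throughout a window the time is equal. What remains there is selection of patients who keep attending, which is a different problem. It also remains unclear who enters each window, since section 9.1.1 speaks in one place of all follow-up analyses and in another of certain ones.

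Three further inferences go too far. The plan does not say that rates are ruled out: counts are inferred from generic descriptive wording, and the word frequency appears in the sub-analysis. It does not say that the last injection marks the end of therapy; it gives no rule at all. And the management objective does not mention subgroups: the subgroup objective concerns patient characteristics, so no planned comparison of visit totals between early and late index years can be cited.

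Finally, this is a descriptive secondary objective with no hypothesis test specified for it. That limits the weight of the point but does not supply the missing denominator.

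**Conclusion.** The concern holds for two outputs: the whole-period summary of visits, treatments and procedures, and the before/after Q3 2021 comparison. Neither has a stated person-time denominator, and as described neither can separate how often patients are seen from how long they are observed. Under one constant rate, counts differ fivefold between 12 and 60 months of observation (60/12), and this ratio does not depend on the assumed rate. The 3.8 ratio compares calendar periods, not patient-time actually observed. The variance share of 76% to 90% rests on assumed visit rates and a simplified follow-up distribution.

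The fixed windows are sound in principle for patients observed throughout, but need a stated entry rule, and the longer ones speak only for patients who stayed. Time on therapy lacks a definition and a censoring rule. The plan should be changed, although no primary objective is affected.

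**What to change.** In section 9.7.1, keep the counts and add:

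- Pooled rates, as total events over total patient-years observed, for visits, treatments and procedures: overall, by year since index, and before and after Q3 2021, with each patient's time split at the end of September 2021. Pooling avoids unstable individual rates when follow-up is short.
- Exclusion of the index visit from the numerator.
- A statement that ending follow-up at the last visit biases rates upward, with a sensitivity analysis that extends observed time past the last visit, for example to the data cut or a fixed interval, whichever is earlier.
- A statement that each 12 to 60 month window includes only patients observed for all of it, with the number included, and that the longer windows describe patients who kept attending.
- For time on therapy, a definition of being on treatment, with patients still on treatment at their last visit or at the data cut treated as censored. A Kaplan-Meier median then suits better than a simple mean.

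The cost is protocol wording and a little more analysis. Time from index to last record is already defined in section 9.3.3.1 as months of history. The downside is that the rates depend on the chosen end of observation, which the sensitivity analysis makes visible.

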NIS Protocol Template

Study number: 1484.0014

Page 17 of 30

Document number: <insert>

- **Increase in the size of GA lesion will be assessed over time.** The size of GA lesion will be further defined following feasibility of data availability, with the basis of the lesion size defined using text field extracts. An example of text entries available for classification are defined below. Note that any analysis involving lesion size will need to be run on a subset population where these data are available/documentated;
Small: “Non-Central Geographic Atrophy, Small.”;
Medium: “Moderate Geographic Atrophy (Juxtafoveal)”;
Large: “1.5 DD Central Geographic Atrophy, Large.”, “Central Geographic Atrophy, Large.”, “4+ Geographic Atrophy.”
- **Progression of GA by Visual Acuity**

Change in visual acuity over time will be tracked from the incident date of GA, and assessed on a yearly basis in order to track the progression of GA over time. In this study, visual acuity will be defined as follows:

[REDACTED] receives VA data from Snellen charts in over 98% of cases, with some other types (ex. Jaeger, charts) in the remainder. There are no instances of ETDRS being received since all data are coming from private retina clinics. All VA entries are standardized and converted to LogMAR for reporting purposes. [REDACTED] standard output for VA is in the form of [REDACTED]

[REDACTED] will only compare VA results of a patient if vision is taken by the same measurement method; i.e., if a patient has their vision recorded using a DCC measurement at index diagnosis, for the remainder of the study, only DCC measurements will be accepted for comparison. This is done to ensure that any change in VA is due to actual change in the patients' vision, and not due to them taking a different vision test. Further, where DCC is not available for VA, any other measurements will be used, ensuring the same type of measurement will be used for the same eye to estimate the changes over time. The ranking order for measurement types is DCC ->NCC ->PH ->DSc ->NSc.

When capturing VA at different time points of interest, a buffer is allowed on either side of the date to increase the chances of each eye coming in for a visit. Should an eye have 2 readings inside the buffer window, the reading closest to the date of interest is taken. The buffers are proposed as follows:

- Index Diagnosis: +/- 30 days
- Follow up reading at Month 6, 12, or 18: +/- 30 days

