- Follow up reading at Month 24, 36, 60: +/- 60 days

Incidence (new cases) and prevalence of GA will be captured, based on the ICD 10 diagnosis codes. On a calendar basis, all newly diagnosed patients will be identified and count as incident patients. Patients with a previous diagnosis of GA in the past years (with respect to a given calendar year), will be counted as prevalent cases during that calendar year.

The yearly counts of newly diagnosed or prevalent cases, will help to understand the progression of the overall disease.

BOEHRINGER INGELHEIM Group of Companies**NIS Protocol Template****Study number: 1484.0014****Page 18 of 30****Document number: <insert>****9.3.2.2 Secondary outcomes****• Retinal Disease Related HCRU Outcomes**

Change in physician care over time will be evaluated from the incident date of GA, and assessed on a yearly basis in order to assess if physician habits have changed over time, particularly following September 2021 and additionally following [REDACTED].

Patient visits: A patient visit (or encounter) is identified in the database any time a patient visits one of the panel physicians. Since the [REDACTED] database consists only of private practicing retina specialists, these are the only types of visits analyzed in the study.

If a patient visits the physician at a hospital, institution, or has an emergency room admission, the event will not be captured. For all patient visits, it is assumed that both eyes are being seen/assessed even in the primary visit reason is for one particular eye. In this sense, all visits will contribute to both eyes and any outcomes at these visits will be available for assessment.

Treatments: The documentation includes **all treatments** including injections, laser treatments, and other procedures. The type of diagnostic procedure done, and the results of these diagnostics are also recorded for most encounters. For any visit, it is assumed that both eyes are being seen, even if only one eye receives any treatment.

Other medical procedures: for example, cataracts removal, eye lid (ptosis correction), etc.

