9.7 DATA ANALYSIS

9.7.1 Main analysis

All analysis will be performed individually on the study population(s). All study results will be provided in tables, and key findings will be highlighted and summarized. The analyses will be conducted at both the patient and patient eye level, as appropriate.

Analysis for objective:

To describe the characteristics* of patients with GA in at least one eye.

To describe characteristics* of the study eye and the fellow eye, at index diagnosis (i.e., proportion of patients with GA in the fellow eye, [REDACTED]

All demographics, and clinical characteristics will be summarized at the index diagnosis date (first diagnosis of GA in the study eye).

Characteristics include demographics, comorbidities, comedications (patient level).

And at eye level; AMD, GA, eCNV, other ocular comorbidities, functional parameters i.e. VA. As well as treatments administered prior to or at index.

Summary will include descriptive statistics; continuous variables will consist of mean (SD) and median (IQR) while categorical variables will be described using frequency and proportion. Absolute numbers (n) of the variables (either yes or patients as appropriate) will be always included in the description of the results.

Analysis for objective:

To evaluate and characterize the progression of newly diagnosed patients with GA during a 5-year follow-up period. To describe patients' characteristics, study eye and the fellow eye characteristics, [REDACTED]

[REDACTED] or progression of the GA lesion in the study eye. To evaluate changes in VA, to evaluate changes in the lesion location, and lesion size (where available).

Patients with GA will be analyzed as an overall group. Subgroups will be also analyzed separately: only GA, GA and wAMD, GA and other comorbidities, and bilateral GA at baseline.

Ocular comorbidities will also be tracked longitudinally (yearly) from index date (GA diagnosis in the database) to better understand the disease journey.

Disease progression will be analyzed at both patient and each individual eye level.

Progression to dry AMD, to GA and to wAMD will be assessed independently using time to event analysis, and also the rate of progression that is seen in the study (2nd, 3rd, 4th, and 5th) years. Bilateral GA eyes at baseline will be evaluated for progression to wAMD

BOEHRINGER INGELHEIM Group of Companies**NIS Protocol Template****Study number: 1484.0014****Page 23 of 30****Document number: <insert>**

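### Characteristics meant to explain progression are taken in the year of progression, with no rule that they precede it, so some may be its consequences

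*Combined protocol and SAP*

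**What the plan says.** The rule is in section 9.7.1, under the secondary objective on comparing progression subgroups. The visible example of the outcome is developing eCNV or not; the events that define groups 1 and 2 are blacked out. Group 3 contrasts subfoveal with extrafoveal lesions.

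- Aim: "Subgroups will be compared against one another to identify any differences in populations leading to progression".
- Timing: "The characteristics will be extracted at the time of assignation to the group". The worked example has a patient without the event in year 1 supplying year-1 values to the non-progressors, and a patient with the event at year 5 supplying year-5 values to the progressors.
- Use: chi-squared tests or SMDs, and then "Following univariate analysis on each metric, a multivariate logistic regression model will be run including relevant metrics identified in the univariate analysis".

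No covariate list is given for this model. For the baseline objective, the same section defines the eye-level characteristics: "And at eye level; AMD, GA, eCNV, other ocular comorbidities, functional parameters i.e. VA". The notes on patient demographics at index and follow-up, later in 9.7.1, add diagnoses in both eyes and lesion location and size.

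Other timing rules stand elsewhere. Section 9.3.3.1 captures changes in clinical characteristics and ocular comorbidities at the first prevalent visit of each calendar year. Sections 9.3.3.2 and 9.3.3.3 fix diabetes, cataract, smoking and alcohol at or before index. Section 9.7.1 allows Kaplan-Meier or Cox methods for disease progression as an option and does not attach them to this comparison.

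**The concern.** A variable can be said to lead to an event only if it is measured before the event. Here the stated interpretation is predictive, but the measurement time for progressors is tied to the event. A characteristic unrelated to later progression can differ between the groups because it changed at or after conversion, pass the univariate screen and enter the logistic model. It would then be reported as a difference leading to progression.

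At stake is the interpretation of one secondary objective, the one meant to explain which GA patients convert. The primary descriptive objectives are not affected.

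**Working it through.** The plan states no effect size, SD or target for this comparison, so there is no figure of its own to reproduce. The check has two parts: what the text permits, and what follows if a value is taken after the event.

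**1. What year k can mean for a progressor**

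| Reading | Value relative to the event | Support in the text |
|---|---|---|
| Visit at which progression is recorded | At the event | Wording of 9.7.1 |
| Anniversary of index | Can be after the event | VA windows in 9.3.2.1: ±30 days at month 12; "Follow up reading at Month 24, 36, 60: +/- 60 days"; none given for month 48 |
| First prevalent visit of the calendar year | At or before a conversion in that calendar year | 9.3.3.1, but 9.7.1 does not refer to it |

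Only the third reading tends to place values before the event. It is not invoked here, and even then the value may come from the conversion visit itself. The limitations in section 9.9 do not mention the issue.

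**2. Size of the artefact, using VA as the example**

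These inputs are assumptions, not from the documents: a fall of d letters caused by conversion and a between-patient SD of s. VA before the event is taken to be unrelated to progression.

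- SMD = d/s.
- For two normal groups with equal variance, the log-odds is linear in VA with slope d/s², so the odds ratio per 10 letters worse is exp(10d/s²).

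| d | s | SMD | Odds ratio per 10 letters worse |
|---|---|---|---|
| 2 | 20 | 2/20 = 0.10 | exp(20/400) = 1.05 |
| 5 | 20 | 5/20 = 0.25 | exp(50/400) = 1.13 |
| 10 | 20 | 10/20 = 0.50 | exp(100/400) = 1.28 |

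For d = 5, an SD of 15 gives 5/15 = 0.33 and an SD of 25 gives 5/25 = 0.20.

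**3. Does comparing within the same year help?**

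A simulation drew the year of progression independently of every index characteristic. It used 72,718 patients (the feasibility count in section 9.5). The other inputs were assumed: yearly progression of 5% or 10%, index VA with mean 60 and SD 20, a drift of −2 letters a year, and measurement SD 5. The SD at a visit is √(20² + 5²) = 20.6, so the expected SMDs are 5/20.6 = 0.24 and 10/20.6 = 0.49 in size. Both groups were taken from the same year, for each of years 1 to 5.

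| VA loss caused by progression | Same-year SMD, progressors minus non-progressors |
|---|---|
| 0 letters | −0.01 to 0.02 |
| 5 letters | −0.26 to −0.20 |
| 10 letters | −0.51 to −0.47 |

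With index VA in place of same-year VA, the SMD was −0.02 to 0.04 in every scenario. This is the correct answer, since nothing at index predicts progression in the simulation. Same-year comparison equalizes follow-up time but leaves the order of cause and effect as it was.

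**The case against.** The strongest reply is that the exposure is narrower than it looks. The objective is to describe and compare, and describing patients at conversion is legitimate. No covariates are named. The eye-level list that contains VA and eCNV belongs to the baseline objective, while the abstract and section 9.3.2.1 treat VA as an outcome. Diabetes, cataract, smoking and alcohol are defined at or before index. The first-prevalent-visit rule in 9.3.3.1 would place some values at or before conversion. The events behind groups 1 and 2 are blacked out, and if one is in the fellow eye, study-eye VA need not fall because of it. Cox regression is already permitted. Finally, the illustration returns its own assumptions.

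Much of this stands and limits the point. VA is a possible candidate, not a stated one, and the figures show a mechanism, not an estimate. But the plan goes beyond description: it says the comparison is to find what leads to progression, and it specifies a screening step and a model. No rule confines the candidates to variables fixed at index, and 9.7.1 does not say whether the index definitions or the time-of-assignment rule prevails. The 9.3.3.1 visit rule and the Cox option are not connected to this analysis, so neither is a safeguard.

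**Conclusion.** The point holds for groups 1 and 2 and for time-varying characteristics that progression can alter: other eye diagnoses, ocular comorbidities, lesion location or size, and VA if it is a candidate. These may be consequences of progression and appear as its predictors, and same-year comparison does not prevent it. Group 3, which no progression event defines, and fixed traits such as sex are outside the point. The size depends on values the documents do not give. An SMD of 0.25 rests on an assumed 5-letter loss and SD 20, with no true association. The plan should be corrected on this point, but it concerns one secondary objective.

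A reader might infer more, in four ways that the documents do not support:

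- **That nearly all VA readings follow conversion.** This needs the anniversary reading, which is one of three, and a window for every year; month 48 has none.
- **That treatments are candidate predictors.** The treatment items in 9.7.1 stand in a list of outputs.
- **That eCNV would be entered as a predictor of itself.** The text speaks only of relevant metrics.
- **That the groups also differ because they are measured in different years.** The plan does not say how years 1 to 5 are combined, and on the natural same-year reading this shift disappears.

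**What to change.** In the progression-subgroup analysis of section 9.7.1:

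1. Take all model covariates at index, or at the start of each yearly at-risk interval, before the event.
2. Let each patient leave the risk set at progression or last visit. Cox regression, already permitted in 9.7.1, or logistic regression by year interval would do this.
3. Reconcile this timing with the at-or-before-index definitions of diabetes, cataract, smoking and alcohol in 9.3.3.2 and 9.3.3.3.
4. Report values at progression only in a separate descriptive table, outside the model.

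The cost is protocol wording and a different model specification, with no new data. The drawback is that index or lagged values do not describe a patient's status at conversion; the descriptive table covers that.
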